# **Summary of Changes from Previous Version:**

Affected Section(s)	Summary of Revisions Made	Rationale

### STATEMENT OF COMPLIANCE

The trial will be conducted in accordance with International Conference on Harmonisation Good Clinical Practice (ICH GCP), applicable United States (US) Code of Federal Regulations (CFR), and the Northwell Health Terms and Conditions of Award. The Principal Investigator will assure that no deviation from, or changes to the protocol will take place without prior agreement from the Investigational New Drug (IND) or Investigational Device Exemption (IDE) sponsor, funding agency and documented approval from the Institutional Review Board (IRB), except where necessary to eliminate an immediate hazard(s) to the trial participants. All personnel involved in the conduct of this study have completed Human Subjects Protection and ICH GCP Training.

The protocol, informed consent form(s), recruitment materials, and all participant materials will be submitted to the IRB for review and approval. Approval of both the protocol and the consent form must be obtained before any participant is enrolled. Any amendment to the protocol will require review and approval by the IRB before the changes are implemented to the study. All changes to the consent form will be IRB approved; a determination will be made regarding whether a new consent needs to be obtained from participants who provided consent, using a previously approved consent form.]

# 1 PROTOCOL SUMMARY

#### 1.1 SYNOPSIS

Title:	Application of Mild Hypothermia for COVID-19 Acute Respiratory Distress Syndrome (ARDS)
Study Description:	Some patients with COVID have abnormally high carbon dioxide and low oxygen levels despite being on the ventilator. The hypothesis of the study is that the application of mild hypothermia to patients with COVID will decrease their metabolic rate and improve their oxygenation and carbon dioxide levels.
Objectives:	
Endpoints:	
 
Primary Objective: To determine if the application of mild hypothermia will decrease the patient's metabolic rate and improved carbon dioxide and oxygenation levels
 
Secondary Objectives: To determine if the application of mild hypothermia reduces the pro-inflammatory response to COVID-19
 
Primary Endpoint: (1) Changes in metabolic requirement during and after hypothermia, (2) Changes in oxygen requirements and levels during and after hypothermia, (3) Changes in carbon dioxide levels during and after hypothermia
 

Study Population:	Secondary Endpoints: (1) Changes in inflammatory markers, CRP, ESR, D- Dimer, Ferritin, during and after hypothermia This study aims to enroll 20 patients, 18 years or older who are admitted to North Shore University Hospital with critical COVID-19 illness requiring intubation.
Phase:	N/A
Description of	North Shore University Hospital will be the only enrolling site. It is a 766
Sites/Facilities Enrolling	bed tertiary care hospital located in Long Island, New York.
Participants:	
Description of Study	Study patients will undergo mild hypothermia to 34.5°C utilizing the Arctic
Intervention:	Sun Temperature Management System (Bard Inc., Louisville, Colorado). The Arctic Sun is a non-invasive targeted temperature management system used to modulate patient temperature with precision by circulating chilled water in pads directly adhered to the patient's skin.
Study Duration:	2 months
Participant Duration:	4 days

# 1.2 SCHEMA

# Day 1 Screening

•Total n= 20

- •Obtain informed consent
- •Screen potential participants by inclusion and exclusion criteria
- •Obtain history, document

# Day 1

# Begin hypothermia

•Perform indirect calorimetry, arterial blood gas, CRP, ESR, D-Dimer, Ferritin prior to hypothermia

•CBC, basic metabolic profile, magnesium, phosphorus, coagulation profile to be drawn every 12 hours during hypothermia.

# Day 2

# Continue hypothermia

•Perform indirect calorimetry, arterial blood gas, CRP, ESR, D-Dimer, Ferritin

•CBC, basic metabolic profile, magnesium, phosphorus, coagulation profile to be drawn q12 hours during hypothermia.

•Perform indirect calorimetry, arterial blood gas, CRP, ESR, D-Dimer, Ferritin prior to rewarming

# End of study assessments

•Perform indirect calorimetry, arterial blood gas, CRP, ESR, D-Dimer, Ferritin

## 1.3 SCHEDULE OF ACTIVITIES (SOA)

#### The schedule below is provided as an example and should be modified as appropriate.

	Screening/Baseline Day - 1 to Day 1	Day 2	Day 3	Day 4
	Scree			
Procedures				
Informed consent	X			
Demographics	Х			
Inclusion/Exclusion	Х			
Medical history	Х			
Targeted Physical Exam Height/weight/ Pulmonary Status	х	х	Х	х
Hypothermia protocol study intervention	х	х		
Metabolic Rate (Calorimetry)	Х	Х	Х	Х
Temperature	Х	Х	Х	Х
Vital signs (BP, HR, RR)	Х	Х	Х	Х
ABG	Х	Х	Х	Х
Hematology (CBC)	Х	Х	Х	Х
BMP	Х	Х	Х	Х
Magnesium	Х	Х	Х	Х
Phosphorus	Х	Х	Х	Х
Coags	Х	Х	Х	Х
Inflammatory markers (Ferritin, CRP, ESR, D-Dimer)	х	х	Х	х
Concomitant Medication	Х	Х	Х	Х
Ventilator Settings	Х	Х	Х	Х
Adverse Event Review	Х	Х	Х	Х
Complete Case Report Forms (CRFs)	х	х	Х	х

# 2 INTRODUCTION

### 2.1 STUDY RATIONALE

COVID-19 pandemic is an ongoing pandemic caused by severe acute respiratory syndrome coronavirus 2 (SARS-CoV-2). A significant percentage of patients with COVID-19 require invasive mechanical ventilation. However, certain percentage of patients with COVID-19 continues to have inadequate oxygenation and carbon dioxide removal despite being on maximal ventilatory support. As there has not been any treatment to show mortality benefit in patients with COVID-19, current standard of care centers around supportive management. We seek to conduct this study to investigate a possible therapeutic treatment for patients with COVID-19 with critical illness.

### 2.2 BACKGROUND

A significant contributor to the morbidity and mortality from COVID-19 is from the abnormal carbon dioxide and oxygen levels in COVID-19 patients. Metabolic studies done on COVID-19 patients have shown that these patients have abnormally high metabolic rates. High metabolic rates results in increased carbon dioxide production and increased oxygen usage, both of which can result in high

carbon dioxide and low oxygen levels. As some patients with severe COVID-19 continue to have high carbon dioxide levels and/or low oxygen levels despite being on the ventilator, we hypothesize that decreasing the metabolic rate in these COVID-19 patients will help their oxygen and carbon dioxide levels. Mild hypothermia is currently used in comatose survivors of cardiac arrest to improve mortality and neurological outcomes. Mild hypothermia is also an effective way to reduce metabolic demand. We therefore propose to apply mild hypothermia to COVID-19 patients to decrease metabolic rate in order to improve their oxygen and carbon dioxide levels. Although the application for mild hypothermia has been widely adopted in some patient populations, it has never been applied in COVID-19 patients. If we can develop a strategy to help improve the oxygen and carbon dioxide levels in COVID-19 patients, it may lead to improvements in their overall outcomes.

# 2.3 RISK/BENEFIT ASSESSMENT

# 2.3.1 KNOWN POTENTIAL RISKS

- Coagulopathy, infections, arrhythmias, electrolyte abnormalities, skin burns, bruising or skin tears from the placement and/or removal of the cooling pads
- There are no known or anticipated long- range risks for this study
- The above stated risks are from the application of hypothermia. There are no known noninvasive treatment options for COVID-19 patients who remain hypoxic and/or hypercarbic on maximal ventilatory support. Extracorporeal Membrane Oxygenator Support (ECMO) is a possible invasive treatment that may be considered; however, ECMO is a highly invasive procedure and most patients do not qualify for ECMO.

# 2.3.2 KNOWN POTENTIAL BENEFITS

- Inducing hypothermia may decrease metabolic demand, improve oxygenation, improve level of carbon dioxide production and decrease the need for ventilatory support
- Potential long term benefits include a decreased morbidity and mortality from COVID-19 infection

# 2.3.3 ASSESSMENT OF POTENTIAL RISKS AND BENEFITS

There are no known non-invasive treatment options for COVID-19 patients who remain hypoxic and/or hypercarbic on maximal ventilatory support. Extracorporeal Membrane Oxygenator Support (ECMO) is a possible invasive treatment that may be considered; however, ECMO is a highly invasive procedure and most patients do not qualify for ECMO. This study aims to investigate the use of hypothermia as a possible noninvasive treatment for patients with COVID-19 who are failing maximal mechanical ventilatory support.

# **3** OBJECTIVES AND ENDPOINTS

OBJECTIVES	ENDPOINTS	JUSTIFICATION FOR ENDPOINTS
Primary		
To determine if the application of mild hypothermia will decrease the patient's metabolic demand and improve carbon dioxide and oxygenation levels	
 
(1) Changes in resting metabolic rate during and after hypothermia
 
(2) Changes in arterial pO2 during and after hypothermia
 
(3) Changes in arterial pCO2 levels during and after hypothermia
 
	Resting metabolic rate is considered the gold standard way to measure metabolic demand. Arterial pO2 and pCO2 are the accepted measurements for oxygen and carbon dioxide levels.
Secondary		
To determine if the application of mild hypothermia reduces the pro- inflammatory response to COVID- 19	Changes in CRP, ESR, D-Dimer, Ferritin, during and after hypothermia.	CRP, ESR, D-Dimer, and Ferritin are inflammatory markers that are have been demonstrated to be elevated in patients with COVID-19 and have been correlated to severity of disease

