### 4 STUDY DESIGN

### 4.1 OVERALL DESIGN

The hypothesis of this study is that the application of mild hypothermia to patients with COVID-19 will decrease their metabolic rate and improve their oxygen and carbon dioxide levels. This is a single site pilot study of 20 subjects. Subjects will be placed on therapeutic hypothermia for 48 hours. Changes in metabolic rate, and levels of oxygen and carbon dioxide will be compared before, during, and after hypothermia.

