# 9 STATISTICAL CONSIDERATIONS

# 9.1 STATISTICAL HYPOTHESES

Primary Efficacy Endpoint(s): (1) Decrease in metabolic rate to 10% during and after hypothermic period as compared to baseline metabolic requirement, (2) Increase in oxygen levels during and after hypothermia as compared to baseline oxygen levels, (3) Decrease in carbon dioxide levels during and after hypothermia as compared to baseline carbon dioxide levels

• Secondary Efficacy Endpoint(s): Decreased inflammatory markers (CRP, ESR, D-Dimer, Ferritin) during and after hypothermia as compared to baseline

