#### 9.4 STATISTICAL ANALYSES

### 9.4.1 GENERAL APPROACH

The following variables will be examined: Changes in metabolic rate, changes in pO2, changes in pCO2, and changes in inflammatory markers.

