# 9.4.2 ANALYSIS OF THE PRIMARY EFFICACY ENDPOINT(S)

The metabolic rate, p02, and pCO2 during each time point after induction of hypothermia will be compared to baseline using the Wilcoxon rank sum test.

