#### 9.4.4 SAFETY ANALYSES

Safety endpoints will be reported as summary statistics.

9.4.5 N/A	BASELINE DESCRIPTIVE STATISTICS
9.4.6 N/A	PLANNED INTERIM ANALYSES
9.4.7 N/A	SUB-GROUP ANALYSES
1	TABULATION OF INDIVIDUAL PARTICIPANT DATA is a pilot study, individual participant data will be listed by measure and time point.

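### The synopsis names oxygen requirement in primary endpoint (2), but the sections that define and test it use raw arterial pO2 alone, so a change in FiO2 can hide or mimic a gain

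*Combined protocol and SAP*

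**What the plan says.** Endpoint (2) is worded differently in different parts of the protocol.

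- Section 1.1 (Synopsis): "Changes in oxygen requirements and levels during and after hypothermia".
- Section 3: "Changes in arterial pO2 during and after hypothermia". Endpoint (3) is likewise arterial pCO2 alone.
- Section 4.1: "levels of oxygen and carbon dioxide will be compared before, during, and after hypothermia".
- Section 9.1: "Increase in oxygen levels during and after hypothermia as compared to baseline oxygen levels".
- Section 9.4.1, the variables to be examined: "Changes in metabolic rate, changes in pO2, changes in pCO2, and changes in inflammatory markers".
- Section 9.4.2 takes metabolic rate, pO2 and pCO2 together; its closing words are "pCO2 during each time point after induction of hypothermia will be compared to baseline using the Wilcoxon rank sum test".

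Ventilator data are collected. Section 8.1 lists delivered oxygen percentage, rate, tidal volume, PEEP and plateau pressure. Sections 1.3, 6.4 and 7.1 also call for settings to be documented. None of these variables appears in Section 9. Sections 2.3.2 and 8.1 raise the possibility that support will be reduced if the treatment helps. Section 6.3 (randomization and blinding) is marked N/A. Section 5.1 already uses pO2/FiO2, below 150, as one of its alternative entry criteria.

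**The concern.** Arterial pO2 in a ventilated patient depends on the lungs and on the oxygen being delivered. If a patient improves and FiO2 is lowered in response, pO2 may not move, and the planned comparison reports no change. If FiO2 is raised, pO2 can go up with no improvement in gas exchange. With one unblinded group there is no comparator to show which of these happened.

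The synopsis wording would have guarded against this, because a fall in oxygen requirement is how a gain shows itself when FiO2 is reduced. That half of the endpoint is missing from every section that defines or tests it. Raw pCO2 is exposed in the same way to changes in ventilation.

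**Working it through.** The plan gives no effect size, variability or power for pO2 or pCO2 (Section 9.2 is N/A), so there is no figure to reproduce. Starting values below are assumptions unless a section is named.

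**1. Oxygen.** By definition, pO2 = P/F × FiO2.

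- Hidden gain: 120 × 0.60 = 72 and 160 × 0.45 = 72. P/F has risen by one third and raw pO2 shows nothing.
- Mimicked gain: 120 × 0.60 = 72 and 120 × 0.80 = 96. P/F is unchanged and raw pO2 rises by one third.
- Break-even: a relative P/F gain g is cancelled by a relative FiO2 cut of g/(1+g). For g of 10%, 20% and 30% the cuts are 9%, 17% and 23%.
- Partial masking: with a 20% gain, FiO2 cuts of 5%, 10% and 16.7% leave raw pO2 at 1.20 × 0.95 = 1.14, 1.20 × 0.90 = 1.08 and 1.20 × 0.833 = 1.00 times baseline.
- Ceiling on mimicry: FiO2 cannot exceed 1.00. At constant P/F, a patient starting at 0.90 can show at most 1.00/0.90 − 1 = 11%. Masking has no such ceiling.

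**2. Carbon dioxide.** At a fixed dead-space fraction (assumption), PaCO2 is proportional to CO2 production divided by minute ventilation. Section 9.1 states "Decrease in metabolic rate to 10% during and after hypothermic period"; I read this as a 10% fall and assume CO2 production falls equally. From the Section 5.1 entry value of 55 mmHg, 55 × 0.90 / v gives:

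| Cut in minute ventilation | v | pCO2 (mmHg) |
|---|---|---|
| 0% | 1.00 | 49.5 |
| 5% | 0.95 | 52.1 |
| 10% | 0.90 | 55.0 |
| 15% | 0.85 | 58.2 |

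The same fall in CO2 production can therefore look like benefit, no change or harm. But this example starts from a fall in metabolic rate, which endpoint (1) measures directly: Sections 6.1.1 and 8.1 provide indirect calorimetry at baseline, on both days of hypothermia and after rewarming.

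**3. Does P/F alone solve it?** I assumed a shunt model with unchanged lungs: shunt uniform on 25–40%, haemoglobin 10, arteriovenous oxygen difference 4 mL/dL, pCO2 55, 12% measurement noise, 20 patients, two-sided 5%. A result counted as false benefit only if the median moved in the favourable direction. FiO2 was cut from 0.80 to 0.60 in all 20.

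- P/F moves by −9% at 25% shunt and +19% at 40% shunt; raw pO2 falls by 10–31%.
- False benefit on P/F: about 16–24% of trials by rank sum and 41–54% by signed-rank. The spread comes from modelling details that the documents do not settle.
- False benefit on raw pO2: 0%.

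Thus P/F recovers gains that raw pO2 hides, but brings false positives in the direction of change the protocol anticipates.

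**4. Timing of settings.** Section 8.1 puts blood gases every 12 hours. Section 1.3 schedules ventilator settings by day, and Sections 6.4 and 8.1 give no time for them. Only Section 7.1, at discontinuation, collects settings and blood gas together.

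**The case against.** **These patients are on maximal support, so FiO2 cannot rise much.** Section 2.3.3 describes them so, but Section 5.1 does not require it: entry is possible on pCO2 or plateau pressure alone. Where it is true it limits mimicry, as the ceiling above shows. It does not limit masking.

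**This is a small feasibility pilot, and "individual participant data will be listed by measure and time point" (Section 9.4.8).** That limits the harm. Even so, Section 9.4.2 prespecifies tests, and any adjustment made from listings would be chosen after seeing the data.

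**Raw pO2 is the cautious choice.** If support falls and the lungs are unchanged, raw pO2 gives no false benefit while P/F can. This stands. A reader might infer that P/F should simply replace pO2; the calculation above does not support that.

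**The CO2 problem is already covered.** In large part this stands. A reader might infer that endpoint (3) is as exposed as endpoint (2), or that a real fall in CO2 production would go unseen. The calorimetry endpoint answers that. What remains is that the pCO2 comparison by itself can mislead.

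**Oxygen requirement might mean consumption rather than FiO2.** Endpoint (1) in the synopsis already covers metabolic requirement, so delivered oxygen is the more natural reading. Either way, the word is absent from Sections 3 and 9.

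**Conclusion.** The point holds and should be fixed before analysis. Endpoint (2) is inconsistent between the synopsis and Sections 3 and 9, and the version that will be tested leaves out the quantity that separates a change in gas exchange from a change in delivered oxygen. The size is an identity for a single patient: a one-third gain can read as zero, and zero can read as a one-third gain. The mimicry example also assumes that P/F stays constant as FiO2 changes, which is a simplification.

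A reader might infer that the trial's oxygen result will be wrong. The documents do not support that: they speak of reduced support only as a possibility and give no frequency for FiO2 changes in either direction, so the chance of a misleading result cannot be derived and the simulated percentages are illustrative. Nor is the necessary information uncollected; the gap lies in endpoint definition, analysis and the timing of recorded settings. The pCO2 limb is secondary. The choice of an unpaired test for within-patient data is a separate matter.

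**What to change.** (a) Reconcile Section 1.1 with Sections 3, 9.1, 9.4.1 and 9.4.2 by restoring oxygen requirement to endpoint (2). Analyse change from baseline in FiO2, in PaO2/FiO2 and in raw pO2, and say that the three are interpreted jointly, with none replacing the others.

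(b) At each time point report how many patients had FiO2 below, equal to and above baseline, together with PEEP.

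(c) Keep arterial pCO2 as endpoint (3) and report it beside delivered minute ventilation (rate × tidal volume) as descriptive support only.

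(d) State that the FiO2, PEEP, rate and tidal volume used are those in force at each arterial blood gas.

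Cost: wording in the endpoint and analysis sections, plus a short rule on when settings are recorded, because the present schedule fixes them only by day. If settings are logged less often than blood gases, (d) means some additional charting. The variables themselves are already listed for collection, and P/F is already used at entry. The downside is that P/F varies with FiO2 and PEEP and can show false benefit when FiO2 is cut, so it must not stand alone. No change to ventilator management is proposed.

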### 4 STUDY DESIGN

### 4.1 OVERALL DESIGN

The hypothesis of this study is that the application of mild hypothermia to patients with COVID-19 will decrease their metabolic rate and improve their oxygen and carbon dioxide levels. This is a single site pilot study of 20 subjects. Subjects will be placed on therapeutic hypothermia for 48 hours. Changes in metabolic rate, and levels of oxygen and carbon dioxide will be compared before, during, and after hypothermia.

## 4.2 SCIENTIFIC RATIONALE FOR STUDY DESIGN

Therapeutic hypothermia is routinely used in patients post cardiac arrest and in patients with cerebral edema secondary to a neurological injury. It has, however, not been used in patients with COVID-19. This study is therefore designed as a small scale pilot study in order to evaluate the feasibility and design of the study and the possible efficiency of hypothermia on COVID patients.

### 4.3 JUSTIFICATION FOR DOSE

The duration of hypothermia for this protocol is 48 hours. This duration is based on existing protocols for the use of hypothermia in non-responsive post-cardiac arrest patients and in patients with cerebral edema after a neurological event.

The degree of hypothermia for this protocol is 34.5°C. This temperature is based on existing protocols for the use of hypothermia in non-responsive post-cardiac arrest patients and in patients with cerebral edema after a neurological event.

## 4.4 END OF STUDY DEFINITION

A participant is considered to have completed the study if he or she has completed all phases of the study including the last scheduled test shown in the Schedule of Activities (SoA), Section 1.3.

The end of the study is defined as completion of the last test shown in the SoA in the trial.

### 5 STUDY POPULATION

### 5.1 INCLUSION CRITERIA

In order to be eligible to participate in this study, an individual must meet all of the following criteria:

- 1. Provision of signed and dated informed consent form from Legally Authorized Representative.
- 2. Stated willingness to comply with all study procedures and availability for the duration of the study
- 3. Male or female, aged 18 years or above
- 4. COVID positive
- 5. On mechanical ventilation with either: refractory respiratory acidosis (ph  $\leq$  7.20), hypercarbia (pCO2  $\geq$  55 mmHg), refractory hypoxia (pO2/FIO2 <150), or plateau pressures >30

## 5.2 EXCLUSION CRITERIA

An individual who meets any of the following criteria will be excluded from participation in this study:

- 1. Bleeding (active bleeding, platelets less than 50,000)
- 2. Uncontrolled cardiac arrhythmia
- 3. History of cryoglobulinemia, major trauma, pregnancy
- 4. Active non-COVID-19 infection that is not controlled with antibiotic or antifungal regimen

# 5.3 5. CONDITIONS THAT WOULD PRECLUDE ACCURATE METABOLIC MEASUREMENT BY INDIRECT CALORIMETRY (RENAL REPLACEMENT THERAPY, PRESENCE OF ECMO, PRESENCE OF CHEST TUBE) LIFESTYLE CONSIDERATIONS

During this study, if participants are on tube feeding, it will be decreased to a trickle feed rate of 10-30 cc/hr. This rate will help to maintain gut integrity and function which is important during the course of critical care illness. Trickle feeds will provide the patients with calories that may pose challenges to calculating the metabolic rate, however as described in literature, some tube feeds are necessary for maintenance of gut performance in critical illness.

### 5.4 SCREEN FAILURES

N/A

# 5.5 STRATEGIES FOR RECRUITMENT AND RETENTION

Patients admitted to North Shore University Hospital with a positive serology test for COVID-19 and who remain in critical care units on advanced life support, mechanical ventilation, will be screened for

inclusion. We anticipate screening at least 10-15 patients daily. There remain over 80 patients with COVID-19 infection at North Shore University Hospital in critical care units.

